6.4.5 Technical Note: Alternative computational strategy

If there are any technical challenges getting the generalized logistic regression model to run in JAGS (the Bayesian statistical software) with missing values for some of the multinomial outcomes, we will use the continuation-ratio model defined by the logits of the events: recurrence-free versus recurrence at 6 months, recurrence-free versus recurrence at 12 months given recurrence-free to 6 months, recurrence-free versus recurrence at 18 months given recurrence-free to 12 months, and recurrence-free versus recurrence at 24-months given recurrence-free to 18-months. Thus, each successive analysis is conditioned on a reduced set of subjects. It can be shown that the multinomial likelihood function decomposes into separate likelihood functions for each of the above conditional contrasts. Importantly, it is computationally easier to estimate separate logistic regression models as opposed to simultaneously needing to estimate the generalized logit model.

The probabilities estimated by the respective logits of the continuation ratio model are given by:

$$\begin{aligned}\eta_{i0} &= \theta_{i1} + \theta_{i2} + \theta_{i3} + \theta_{i4} \\ \eta_{i1} &= (\theta_{i2} + \theta_{i3} + \theta_{i4}) / (\theta_{i1} + \theta_{i2} + \theta_{i3} + \theta_{i4}) \\ \eta_{i3} &= (\theta_{i3} + \theta_{i4}) / (\theta_{i2} + \theta_{i3} + \theta_{i4}) \\ \eta_{i4} &= \theta_{i4} / (\theta_{i3} + \theta_{i4})\end{aligned}$$

or equivalently

$$\begin{aligned}\theta_{i0} &= 1 - \eta_{i1} \\ \theta_{i1} &= \eta_{i1}(1 - \eta_{i2}) \\ \theta_{i2} &= \eta_{i1}\eta_{i2}(1 - \eta_{i3}) \\ \theta_{i3} &= \eta_{i1}\eta_{i2}\eta_{i3}(1 - \eta_{i4}) \\ \theta_{i4} &= \eta_{i1}\eta_{i2}\eta_{i3}\eta_{i4}\end{aligned}$$

Because there is a one-to-one relationship between the sets of probabilities, following estimation of the separate logistic regression models we simply need to multiply the necessary probabilities together to recover the probabilities for the multinomial model and thus evaluate the hypothesis test for clinical success.

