Official Title: An Intraoperative Guidance Platform for Radio Frequency Ablation

NCT number: NCT04152343

Document Type: Statistical Analysis Plan

Date of the Document: July 10, 2018

PRINCIPAL INVESTIGATOR:

[name]

Department of Radiology

Section of Interventional Radiology

Dartmouth-Hitchcock Medical Center

[name]

[name]

[contact]

Email: [contact]

As noted in the protocol, the following Statistical Analysis Plan is referenced in the protocol (page 9). The following was obtained from the study SF19108 clinical protocol v29July2019, pages 13-18, Section 6.0 Statistical Plan

6 Statistical Plan

6.1 *Population Size*

Fifty two (52) patients will be recruited in the study, anticipating that up to 4 patients might drop out from the study, leaving a total of 48 patients. Based on prior statistics from [name] clinic, approximately 30% of patients have more than one tumor which is treated. Assuming that 30% of the patients have two tumors,

recruitment of 48 subjects will yield 62 treated individual tumors which will be analyzed. A population of 62 analyzed tumors provides a sufficient statistical power for the outcomes the trial is designed to estimate, given reasonable hypotheses on the effect size that the PGP will result in, as discussed next.

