We refrain from using a Cox model or a parametric survival model to compare the status of the patients at two years of follow-up because reoccurrence status may only be known at 6-monthly intervals. Instead, we use a discrete-time survival model in which we model the probability of reoccurrence in each 6-month period thru 2-years of follow-up along with the event that the length of follow-up without reoccurrence exceeds 2-years. The dependent variable is a polytomous multinomial random variable because each patient's reoccurrence status (if followed up for the full 2 years) will be in exactly one of the 5 categories. The probabilities for the 5 categories sum to 1. The purpose of modeling the interim survival probabilities is that the interim probabilities allow the missing outcome status for patients not followed for two-years to be internally imputed during Bayesian model estimation. This approach allows for maximal use of the information in the data as all subjects are used in the analysis even if that haven't been followed up for two years (emulating what the Cox or other survival model does with continuous-time follow-up data). If we end up measuring reoccurrence status every three months, we will still pursue the described approach (but have 9 categories for the multinomial outcome as opposed to 5 categories) as the data will still not be close enough to continuous to support using the Cox model.

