6.4.2 Model for multinomial outcome: generalized logistic regression

The distribution of y_i is multinomial with five categories:

$$y_i | \theta_i \sim \text{Multinomial}_5(1, \theta_i)$$

where $\theta_i = (\theta_{i0}, \theta_{i1}, \theta_{i2}, \theta_{i3}, \theta_{i4})$ is the vector of probabilities associated with the five possible outcomes for patient i . Models for multinomial outcomes are characterized by the way in which the elements of θ_i are mapped to the predictors. One commonly used specification is generalized logistic regression in which each component of θ_i is compared to all other components through a logit link function by supposing:

$$\theta_{ik} = \lambda_{ik} / (\lambda_{i0} + \lambda_{i1} + \lambda_{i2} + \lambda_{i3} + \lambda_{i4})$$

and $\log(\lambda_{ik}) = \gamma_k + \beta x_i$ for $k = 0, \dots, 4$. A key feature of this specification is that the Bayesian software package JAGS will impute any y_{ik} whose value is missing. To implement this feature any values of y_{ik} that are missing will be represented as NA in the analytic data set. We note that the above specification assumes the proportional odds assumption that the effects of all terms other than γ_k does not depend on k holds. This is an assumption whose legitimacy can be tested empirically.

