6.4.4 Evaluation of hypothesis test and other summaries of the posterior distribution

We wish to average the 2-year survival probability across the study patients, given by

$$q_{\text{RFA}} = 1 - n^{-1} \sum_{i=1}^n \theta_{i4}$$

where based on the above generalized logit model the probability of clinical success at 2-years for patient i is given by

$$\theta_{i4} = \frac{\exp(\gamma_4 + \beta x_i)}{\exp(\gamma_0 + \beta x_i) + \exp(\gamma_1 + \beta x_i) + \exp(\gamma_2 + \beta x_i) + \exp(\gamma_3 + \beta x_i) + \exp(\gamma_4 + \beta x_i)}$$

The posterior probability of clinical success, $\Pr(q_{\text{RFA}} < q_{\text{base}} | y_1, \dots, y_n, x_1, \dots, x_n)$, is then determined by evaluating q_{RFA} for a large number of draws from the posterior distribution of the model parameters and evaluating the Monte-Carlo average

$$\Pr(q_{\text{RFA}} < q_{\text{base}} | y_1, \dots, y_n, x_1, \dots, x_n) \cong n^{-1} \sum_{j=1}^{n_{\text{sim}}} I(q_{\text{RFA}}^j < q_{\text{base}})$$

where q_{RFA}^j denotes the value of q_{RFA} computed on the j th of n_{sim} draws of the model parameters from their joint posterior distribution. The mean, standard deviation, and 95% interval estimates of q_{RFA} will be similarly determined.

Because the chance of clinical success likely varies continuously with tumor size, we can substitute the mean tumor size for the benchmark population in [4] for x_i to essentially control for tumor size. Alternatively, we may substitute x_i with the corresponding small, medium, and large tumor size subgroup mean and in so-doing evaluate the posterior probability with closer control for the tumor size distribution. For the subgroup analyses that compare the performance of RFA-GP on the small, medium and large tumor

subgroups we may estimate $\Pr(q_{\text{RFA}} < q_{\text{base}} \mid \text{size} = s, y_1, \dots, y_n, x_1, \dots, x_n)$ separately for each subgroup $s \in \{\text{small, medium, large}\}$.

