6.4.6 Power for clinical success

In lieu of performing an exact power calculation under the Bayesian model specified above, we will perform an illustrative calculation based on Fisher's exact test. Allowing a type I error of 0.05, the test of the above one-sided hypotheses for q_{RFA} with a sample-size of 62 lesions will reject the null hypothesis with 80% power if $q_{\text{RFA}} < 0.105$. That is, the minimal detectable difference is a reduction of approximately 0.117 in the likelihood of tumor reoccurrence – which is an effect size in line with conservative hypotheses about the improvement in outcomes that the PGP might introduce.

Subgroup analyses (e.g., based on treated tumor size) will require larger effect sizes to retain the same level of power. However, the study is only intended to be powered for the primary analysis.

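### The recurrence fallback in SAP 6.4.5 fits a separate, very sparse regression for each follow-up interval; this is not equivalent to a model with one common tumor-size effect, and it weakens the size-specific and size-standardised results

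*SAP*

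**What the plan says.** SAP 6.4 models 2-year recurrence in 6-month intervals. Section 6.4.2 gives each of the five outcome categories its own intercept and the same size term: log(λ_ik) = γ_k + βx_i for k = 0 to 4. It comments that "the above specification assumes the proportional odds assumption that the effects of all terms other than" the intercepts do not vary with the category. Section 6.4.3 gives all coefficients Normal(0, 10^6) priors.

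Section 6.4.5 is presented as an alternative computational strategy, to be used if JAGS has technical trouble with missing outcomes. It splits the outcome into four conditional contrasts, each fitted on the lesions still recurrence-free. The stated reason is that "it is computationally easier to estimate separate logistic regression models as opposed to simultaneously needing to estimate the generalized logit model". It concludes that multiplying the fitted probabilities recovers those of the multinomial model and hence the hypothesis test. It does not write the four linear predictors, say whether the size slope is shared, give priors, or say what to do when an interval has no recurrence.

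The size relation is used elsewhere. Section 6.4.4 begins its size adjustment with "Because the chance of clinical success likely varies continuously with tumor size" and then substitutes benchmark or subgroup sizes into the model. Section 6.2 says the clinical analyses will be weighted to the benchmark's size distribution. If status is checked every three months, section 6.4 would "have 9 categories for the multinomial outcome as opposed to 5 categories", which makes eight conditional regressions.

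**The concern.** The map between the category probabilities and the conditional probabilities is one-to-one. This does not make two regressions on tumor size the same model. The likelihood can be fitted piece by piece without loss only if the pieces share no parameter. A size effect common to all intervals is such a shared parameter. Fitting the pieces separately gives every interval its own slope, so the fallback changes the model as well as the computation.

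This matters because recurrences are few, the priors give almost no stabilisation, and the trial has no control arm. The benchmark recurrence rates run from 14.1% (small) through 24.5% (medium) to 58.1% (large), so comparability rests heavily on the size adjustment. Four slopes, each resting on a handful of events, are a weak basis for it.

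**Working it through.** **Inputs from the SAP.** 62 lesions (section 6.1: "recruitment of 48 subjects will yield 62 treated individual tumors which will be analyzed"; 48 × 1.3 = 62.4). Null recurrence is 0.2217 (6.4) and the alternative is 0.105 at 80% power, one-sided 0.05 (6.4.6). The printed size mix of 12.9/41.9/45.2% small/medium/large gives 8/26/28 lesions.

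**The plan's own power figure.** With an exact one-sample binomial test that rejects at 8 or fewer recurrences in 62, alpha is 0.0483 at 0.2217 and power is 0.8006 at 0.105. The SAP figure reproduces, so these two rates are a fair range for the expected events.

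**Does 6.4.2 contain a common size effect?** θ_ik = exp(γ_k + βx_i) / Σ_m exp(γ_m + βx_i). The factor exp(βx_i) is in the numerator and in every term of the denominator, so θ_ik = exp(γ_k) / Σ_m exp(γ_m). A numerical check with β = -3, 0 and 2 and sizes 2, 4 and 6 gave identical probabilities. The formula for θ_i4 in 6.4.4 cancels in the same way.

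**Why separate fits differ from a common slope.** Let h_ik be the chance of recurrence in interval k for a lesion that enters it recurrence-free, with logit(h_ik) = a_k + b_k x_i. The likelihood is a product over intervals. If every (a_k, b_k) is free, each factor can be maximised alone. If b_k = b for all k, every factor contains b and they must be fitted together. With continuous size this is 8 parameters against 5.

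**Events per model**, if spread evenly over intervals (an assumption):
- 62 × 0.105 = 6.5, and 6.5 / 4 = 1.6.
- 62 × 0.2217 = 13.7, and 13.7 / 4 = 3.4.
- With an assumed 50/25/15/10% spread: 3.3/1.6/1.0/0.7 and 6.9/3.4/2.1/1.4.
- With eight intervals: 6.5 / 8 = 0.8 and 13.7 / 8 = 1.7.

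**Chance that at least one of four intervals is empty**, with k = q/4 and full follow-up: 4(1-k)^62 - 6(1-2k)^62 + 4(1-3k)^62 - (1-4k)^62. This is 0.58 at q = 0.105 and 0.11 at q = 0.2217.

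**Effect on size-specific recurrence.** This needs assumptions that the documents do not give: sizes from 2.1 to 8 cm, equal interval hazards and a log-odds slope of 0.5 per cm. The benchmark rates have logits -1.81, -1.13 and 0.33. At about 2.5, 4 and 6.5 cm they imply (1.81 - 1.13)/1.5 = 0.45 and (0.33 + 1.13)/2.5 = 0.58 per cm. Fits are maximum likelihood, standing in for near-flat priors. Printed mix, full follow-up, 1,500 trials per setting:

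| Rate, size | Truth | Separate slopes | Shared slope |
|---|---|---|---|
| 0.105, 2.5 cm | 2.4% | 4.5% | 2.9% |
| 0.105, 6.5 cm | 16.2% | 12.9% | 15.3% |
| 0.2217, 2.5 cm | 5.8% | 8.2% | 6.3% |

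A further run under the printed mix gave these root mean squared errors at 2.5 cm, separate against shared:
- Full follow-up: 0.048 against 0.030 (rate 0.105) and 0.054 against 0.039 (rate 0.2217).
- Partial follow-up: 0.103 against 0.045 and 0.158 against 0.056. The follow-up pattern is itself an assumption, so the direction matters more than the exact size.

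The gain at 2.5 cm remained when the true slopes differed by interval. With eight intervals, the mean squared error at 2.5 cm was 3.1 to 4.0 times larger for separate slopes. At 4 cm, with four intervals, the separate fits were no worse (0.029 against 0.032 at rate 0.105).

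**Sensitivity to the size mix.** The SAP's 24.1% benchmark reproduces only if the size weights are reversed; as printed they give 38.3%. With 28/26/8 lesions and full follow-up, the mean squared error ratios are only 1.1 to 1.3. An independent set-up (2.5, 4 and 6 cm, slope 0.6 per cm, reversed mix, rate 0.2217) gave truth 0.107/0.239/0.569, separate 0.123/0.213/0.601 and shared 0.110/0.237/0.568, with nearly equal standard deviations.

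**Overall q_RFA.** 0.103 against 0.104 in the first set-up, and 0.2224 against 0.2229 in the independent one.

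**The case against.** The strongest objection is that nothing is lost from the main model. A reader might infer that the fallback drops a size effect that 6.4.2 has. The documents do not support this: β cancels, so the printed main model gives every size the same recurrence, while separate logits with size can at least show a gradient. In the independent set-up above, a model without size is off by +0.116 for small and -0.346 for large tumors, far more than the separate fits. This stands, and it makes the repair of 6.4.2 the larger job. It does not make the equivalence claim in 6.4.5 correct for the common effect that 6.4.2 declares.

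Other points also carry weight:
- Section 6.4.5 never writes its linear predictors, and 6.4.1 allows size to be left out. Without size, the separate fits are an exact reparameterisation. The concern applies only when size is in the model.
- The fallback is a contingency. Missing outcomes are expected before all lesions reach two years, but 6.4.2 expects JAGS to impute them, so the documents do not show that the fallback will be needed.
- The simulations generate data mostly under a common slope, which favours the shared-slope fit.
- Section 6.4.4 words its size adjustments as options, and 6.4.6 powers only the primary analysis. Against this, section 6.2 commits to size weighting for the clinical outcome.

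**Conclusion.** The point holds, at low priority. Under a common size effect, separately fitted interval regressions are a different and sparser model, and the statement that they recover the same one should go. With 6.5 to 13.7 expected recurrences and near-flat priors, they make size-specific and size-standardised recurrence less precise and somewhat biased. The loss is clearest for small tumors under the printed mix and under partial follow-up. It is small under the reversed mix with full follow-up. These magnitudes rest on the assumed sizes, slope and interval hazards.

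Two stronger readings are not supported. One is that separate slopes always flatten the size gradient and understate large-tumor recurrence. Under the reversed mix, large-tumor recurrence came out at 0.294 against a true 0.296 at the lower rate, and at 0.591 against 0.561 at the higher, so the direction is not general. The other is that the main clinical test is compromised: the unstandardised overall q_RFA is almost unchanged.

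**What to change.** In 6.4.5, replace the separate regressions by one discrete-time logistic model on stacked records, with one record for each interval that a lesion enters recurrence-free and whose status is known. Write out the predictor: logit(h_ik) = a_k + b x_i, with one intercept per interval and a single size slope. Compute q_RFA and the size-specific or standardised probabilities from it. Partial follow-up is then handled without imputing outcome categories. Keep interval-specific slopes only as a check of the common slope, and say how empty intervals are treated.

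Delete the claim that the separate fits recover the same model, and make the η indices agree (0, 1, 3, 4 in one display, 1 to 4 in the other).

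Repair 6.4.2 and 6.4.4 so that size has an identified effect, for example by setting intercept and slope to zero in a reference category. Do not call the stacked model identical to 6.4.2: even after that repair, a common slope on category-versus-reference logits is not a common slope on interval hazards.

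The cost is SAP wording. The downside is the assumption of a common size effect on the interval hazards, which the slope check can examine only weakly with so few events.

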6.4.6 Power for clinical success

In lieu of performing an exact power calculation under the Bayesian model specified above, we will perform an illustrative calculation based on Fisher's exact test. Allowing a type I error of 0.05, the test of the above one-sided hypotheses for q_{RFA} with a sample-size of 62 lesions will reject the null hypothesis with 80% power if $q_{\text{RFA}} < 0.105$. That is, the minimal detectable difference is a reduction of approximately 0.117 in the likelihood of tumor reoccurrence – which is an effect size in line with conservative hypotheses about the improvement in outcomes that the PGP might introduce.

Subgroup analyses (e.g., based on treated tumor size) will require larger effect sizes to retain the same level of power. However, the study is only intended to be powered for the primary analysis.
